9.5.2.1 Primary Endpoint

The primary efficacy endpoint is the proportion of participants who achieve a ≥ 1 -stage improvement (as defined by NASH CRN Fibrosis Score) in fibrosis without worsening of NASH or NASH improvement (as defined by NAFLD Activity Score) with no worsening of fibrosis (as defined by NASH CRN Fibrosis Score) at Week 24, as determined by liver biopsy.

For this protocol, improvement in fibrosis is defined as a decrease of fibrosis by ≥ 1 point, as determined by the NASH CRN Fibrosis Score. Worsening of fibrosis is defined as an increase of fibrosis by ≥ 1 point, as determined by the NASH CRN Fibrosis Score.

Worsening of NASH is defined as an increase of the NAFLD Activity Score (NAS) by ≥ 1 point. NASH improvement is defined as a decrease of NAS by ≥ 2 points (with contribution from > 1 NAS component) (see [Section 8.5.1.1](#)).

Stratification will be defined as follows: One of the strata will have participants from Japan and the other four will correspond to sites in other countries 1: T2DM status (yes) and NAS (≤ 5); 2: T2DM status (yes) and NAS (> 5); 3: T2DM status (no) and NAS (≤ 5); 4: T2DM status (no) and NAS (> 5).

A Cochran-Armitage trend test across proportions at a one-sided 0.05 level of significance will be used to examine the linear trend among the proportions across treatment groups. Also, 95% CIs for the odds-ratio of each BMS treatment group to placebo will be provided.

A sensitivity analysis using an extended Cochran Mantel-Haenszel (CMH) correlation test³⁶ will be used to assess the trend among the proportions for treatment groups with an adjustment to strata. A two-sided 0.10 level of significance will be used.

Since this is a Phase 2 study, no adjustment for multiplicity will be applied.

All participants who prematurely discontinue from treatment without a biopsy at Week 24 (or ET, if applicable) or otherwise have a missing Week 24 (or ET, if applicable) biopsy result will be considered nonresponders for the primary analysis of the primary efficacy endpoint. In addition, a completer analysis of the primary endpoint will be performed excluding participants without a Week 24 biopsy.

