9.5.2.3 Methods for Handling Treatment Discontinuations and Other Causes of Missing Data

Participants who prematurely discontinue study medication will be expected to complete an ET Visit and must continue to be followed for follow-up visits/procedures per the Schedule of Activities (e.g., Week 52/PTFU) (see [Section 1](#)).

Primary efficacy analyses will include all data that are collected on a participant during the study even after treatment discontinuation. All efficacy analyses will be performed with the mITT population, analyzed according to randomized treatment.

Additional details for handling of missing data will be provided in the SAP.

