5.0 Analysis Populations

- Enrolled Population: All participants who sign informed consent.
- Randomized Population: All participants who are randomized, analyzed as per randomized treatment.
- Modified intent-to-treat (mITT) Population: All participants who are randomized and receive at least 1 dose of study treatment, analyzed according to randomized treatment. All primary efficacy analyses will be conducted using this population.
- As Treated (Safety) Population: All participants who are randomized and receive at least 1 dose of study medication, analyzed according to treatment actually received. This population will be essentially the same as the mITT unless a participant received an incorrect treatment, i.e., a treatment different from what he/she was randomized to. All safety analyses will be conducted using this population.

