6.1.1 Primary Efficacy Analysis

The primary efficacy endpoint is the proportion of participants who achieve a ≥ 1 -stage improvement (as defined by NASH CRN Fibrosis Score) in fibrosis without worsening of NASH or NASH improvement (as defined by NAFLD Activity Score) with no worsening of fibrosis (as defined by NASH CRN Fibrosis Score) at Week 24, as determined by liver biopsy.

For this protocol, improvement in fibrosis is defined as a decrease of fibrosis by ≥ 1 point, as determined by the NASH CRN Fibrosis Score. Worsening of fibrosis is defined as an increase of fibrosis by ≥ 1 point, as determined by the NASH CRN Fibrosis Score. Worsening of NASH is defined as an increase of the

Sponsor: Bristol-Myers Squibb

Protocol no: MB130-068

NAFLD Activity Score (NAS) by ≥ 1 point. NASH improvement is defined as a decrease of NAS by ≥ 2 points (with contribution from > 1 NAS component).

A Cochran-Armitage trend test of proportions at a one-sided 0.05 level of significance will be used to examine the linear trend among the proportions across treatment groups. In addition, 95% confidence intervals (CIs) for the odds-ratio of each BMS treatment group to placebo will be provided. The null hypothesis states that there is no association between treatment groups and fibrosis stage improvement. The alternative hypothesis states that there is an association between treatment groups and fibrosis stage improvement. The Cochran-Armitage trend test does not take into consideration stratification factors into the model therefore, further sensitivity analysis will be performed as described below in SAP Section 6.1.1.1.

The proportion of participants with response will be summarized as frequency counts and percentages by randomized strata as well as overall for each treatment group.

Participants who prematurely discontinue from treatment without a biopsy result for NASH CRN Fibrosis Score or NAS at Week 24 (or ET, if applicable) or otherwise have a missing Week 24 (or ET, if applicable) biopsy result will be considered non-responders for the primary analysis of the primary efficacy endpoint.

The primary analysis will be based on the mITT population. In addition, a completer analysis of the primary variable will be performed. Patients with an evaluable Week 24 biopsy results are considered completers. All biopsy results will be included in the participant listings.

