6.1.2 Secondary Efficacy Analyses

All secondary efficacy analyses will be based on the mITT population using the same methodology as the primary efficacy analysis. Since this is a Phase 2 study, no adjustment for multiplicity will be applied. The p-values will be considered descriptive.

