6.4 Exploratory Analyses

Analyses for exploratory endpoints will be performed using the mITT or safety populations.

Exploratory dichotomous response variables will be summarized in a manner similar to that used for the secondary efficacy analyses. In addition, summaries of ≥ 1 stage improvement, no change, and worsening will be tabulated and graphically presented for NASH CRN Fibrosis Score, Ishak Fibrosis Score, and NAS Total at Week 24. For these analyses, participants without a Week 24 or ET result will be classified into the "Worse" category for these exploratory summaries.

Early termination visits for non-biopsy endpoints such as imaging and biomarkers may occur at other time points and will not be summarized together with Week 24. For non-biopsy endpoints, ET will be summarized separately in the summary tables. Imputation on missing data will not be performed for non-biopsy endpoints.

Summary statistics will be tabulated for all treated subjects by treatment and by Visit. Continuous data will be summarized using n, mean, standard deviation, median, minimum, and maximum.

Analysis of covariance (ANCOVA) model will be used to explore change from baseline for endpoints having a baseline and a post-baseline values.

Repeated measures analysis will model the change from baseline for the endpoint in presence of repeated measurements taken at various timepoints on/before the analysis visit.

Sponsor: Bristol-Myers Squibb

Protocol no: MB130-068

The model will include treatment group, visit, baseline value, treatment * visit and baseline stratification factors as main effects. An unstructured covariance matrix will be used to represent the correlation of the repeated measures within each subject. The model will provide point estimates, standard errors and 2-sided 95% confidence intervals for mean change from baseline at by time points.

Other biomarkers will be descriptively summarized by time point and will include percent change from baseline in addition to change from baseline. Exploratory endpoints assessing relationships will be graphically presented.

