7.2 Week 24 Data Analysis

Due to COVID-19 the Week 24 data analysis is based on approximately 160 subjects when planned sample size was reached which occurred at eCRF data cut-off date of May 29 2020. The study will continue to enroll for Week 52 data analysis in a blinded fashion as planned for 197 patients. The level of unblinding and roles to be unblinded will be specified in a separate unblinding study plan that will be finalized prior to the database lock (reference for unblinding plan). The study will continue in a blinded fashion following this analysis. Study data through Week 24 will be analyzed by pre-specified unblinded individuals as specified in the unblinded plan.

- All Efficacy data will be summarized based on mITT principle for DB Lock defined by eCRF date cut-off MAY 29, 2020 on all participants who have completed liver biopsy.
- If the biopsies were delayed and performed between Week 24 and Week 48, the biopsies results will be included in the planned Week 24.
- Safety data will be summarized using Safety population through DB lock defined by eCRF date cut-off May 29, 2020.
- All available data beyond Week 24 will be summarized descriptively.
- SAS datasets and subject level data listings will be shared in accordance with unblinding plan (add reference)

This analysis will include the primary and secondary efficacy endpoints, and selected safety, PK, and exploratory endpoints. The list of tables, figures, and listings (TFLs) to be provided for this analysis will be kept in a separate document outside the SAP.

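### SAP 7.2 can be read as limiting the Week 24 primary analysis to biopsied participants, against SAP 5.0 and 6.1.1, and no supplied passage says whether the run on about 160 or one on 197 is primary

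*SAP*

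**What the plan says.** **Who is analysed.** SAP 5.0 defines mITT as "All participants who are randomized and receive at least 1 dose of study treatment, analyzed according to randomized treatment", with no biopsy condition. SAP 6.1.1 bases the primary analysis on that population. A participant with no Week 24 or early-termination (ET) "biopsy result will be considered non-responders for the primary analysis of the primary efficacy endpoint". The same section adds a separate completer analysis: "Patients with an evaluable Week 24 biopsy results are considered completers". SAP 6.1.2 extends the method to the secondary endpoints: "All secondary efficacy analyses will be based on the mITT population using the same methodology as the primary efficacy analysis".

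The protocol agrees. In Protocol 9.5.2.1 a participant with a missing "biopsy result will be considered nonresponders for the primary analysis of the primary efficacy endpoint", and Protocol 9.5.2.3 states: "All efficacy analyses will be performed with the mITT population, analyzed according to randomized treatment".

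**What the Week 24 run uses.** SAP 7.2 cites COVID-19 and bases this run on roughly 160 participants. Its efficacy bullet invokes the mITT principle and then an "eCRF date cut-off MAY 29, 2020 on all participants who have completed liver biopsy". The run covers the primary and secondary endpoints. Biopsies delayed to between Week 24 and Week 48 are accepted as Week 24 results.

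**When it happens.** Protocol 9.5.7 and SAP 2.5 both tie the Week 24 analysis to all participants having finished; SAP 2.5 refers to 7.2 for details. SAP 7.2 keeps the 197 for the Week 52 analysis. SAP 7.3, which describes that analysis, lists no endpoints and points to an output list held outside the SAP.

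**The concern.** The efficacy bullet in SAP 7.2 names two different sets at once. The mITT principle keeps an unbiopsied participant in the denominator as a failure; the closing words of the bullet remove that participant. Taken literally, the non-responder rule has no unbiopsied participants left to act on, and the primary analysis becomes nearly the completer analysis.

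Two programmers could therefore build different denominators for the primary endpoint from this SAP. If biopsies are missing more often at higher doses, the biopsied-only set raises the responder rates of those arms relative to the planned definition. If they are missing more often on placebo, it shrinks the apparent effect.

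The bullet also leaves open when a biopsy absent on 29 May 2020 is missing and when it is only pending. Finally, a Week 24 result on about 160 and a possible later one on 197 have no stated order.

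**Working it through.** **1. The plan's own figure.** Inputs from Protocol 9.1 and SAP 2.2: 40 per arm, rates 15/20/30/40%, Cochran-Armitage trend test, one-sided 0.05. With scores x = 0, 1, 2, 3 (mean 1.5) and pooled rate 0.2625:

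- T = 40 × Σ(x − 1.5)p = 40 × 0.425 = 17.0
- V0 = 0.2625 × 0.7375 × 40 × 5 = 38.72
- V1 = 40 × Σ(x − 1.5)²p(1 − p) = 40 × 0.9194 = 36.78
- Power = Φ[(17.0 − 1.645 × √38.72)/√36.78] = Φ(1.116) = 86.8%

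Dose scores 0/10/20/40 give 86.1%. The claim of at least 80% is confirmed. On 197 (49/49/49/50) the power is 92.4% with equal scores. The problem is who is analysed, not the sample size.

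**2. The passages side by side.**

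| Source | Set | Unbiopsied participant |
|---|---|---|
| SAP 5.0, 6.1.1, 6.1.2; Protocol 9.5.2.1, 9.5.2.3 | randomized and dosed | kept, counted as failure |
| SAP 6.1.1 completer analysis | evaluable Week 24 biopsy | excluded |
| SAP 7.2, taken literally | completed biopsy at cut-off | excluded |

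**3. Can the 160 be identified another way?** SAP 2.2 uses 160 as the number planned to be randomized. Protocol 6.2, in the version dated 30 January 2020, already reports enrolment closed at 197. So the planned size that SAP 7.2 says was reached on 29 May 2020 cannot be a count of randomizations. Having a biopsy is the only membership criterion given.

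Day 169 is first dose + 168 days, and 29 May 2020 − 168 days = 13 December 2019. Anyone first dosed later had not reached nominal Week 24. Adding the 5-day visit window and the 7-day biopsy window gives 180 days, or 1 December 2019. An absent biopsy at the cut-off could therefore be not yet due, delayed or truly missing.

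**4. Rejection rates with no trend (assumed missingness).** The documents give no missing-biopsy rates. Two gradients are assumed, in the order placebo/10/20/40 mg, sized so that about 160 are biopsied:

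- 44 per arm, 5/7/10/15% missing: 44 × 3.63 = 160 of 176, so 16 drop out
- 46 per arm, 5/10/15/20% missing: 46 × 3.50 = 161 of 184, so 23 drop out

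There were 400,000 simulated trials per scenario, with scores 0-3 and one-sided 0.05. Null (a) holds the non-responder-counted rate flat at r, so response among the biopsied is r/(1 − m), where m is the arm's missing fraction. Null (b) holds response among the biopsied flat at r. The ranges cover r = 15, 20 and 25%.

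| Missingness | Null | Biopsied only | Non-responder rule |
|---|---|---|---|
| 5/7/10/15% | (a) | 8.1-9.4% | 4.9-5.0% |
| 5/10/15/20% | (a) | 10.3-13.1% | 5.0-5.1% |
| both gradients reversed | (a) | 1.6-3.1% | about 5% |
| equal 10% | (a), (b) | 5.0-5.1% | about 5% |
| 5/7/10/15% | (b) | 5.1% | 2.6-3.0% |
| 5/10/15/20% | (b) | 5.1-5.2% | 1.8-2.4% |

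Repeat runs move these figures by at most about 0.2 points.

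**5. Effect size at the planning rates.** Take 15% on placebo and 40% at 40 mg as non-responder-counted, a difference of 25 points. On the biopsied set each rate is divided by (1 − m):

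- Rising: 0.40/0.85 − 0.15/0.95 = 47.1 − 15.8 = 31.3 points; 0.40/0.80 − 0.15/0.95 = 50.0 − 15.8 = 34.2 points
- Equal 10%: (0.40 − 0.15)/0.90 = 27.8 points
- Reversed: 0.40/0.95 − 0.15/0.85 = 42.1 − 17.6 = 24.5 points; 0.40/0.95 − 0.15/0.80 = 42.1 − 18.8 = 23.4 points

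**The case against.** The best defence is that the biopsy phrase is a timing trigger. It sits in the section on the sequence of analyses, and both sibling rules use biopsy completion that way: SAP 7.1 after about 100 biopsies, Protocol 9.5.7 after all of them. The same bullet invokes mITT. SAP 6.4 expects unbiopsied people in the set, since "participants without a Week 24 or ET result will be classified into the" worst category. This stands as the probable intent. It does not remove the contradiction, because a timing rule still has to say who was due by the cut-off, and SAP 7.2 does not.

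Second, SAP 5.0 and 6.1.1 and Protocol 9.5.7 point to the full dosed set as primary, and the output lists and unblinding plan were not supplied. This stands as implication only; nothing in the supplied text names the primary run.

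Third, the missingness gradients are assumed. Protocol 6.3.2.1 and 6.3.2.3 report no discontinuations from gastrointestinal events in Phase 2a, and none from injection-related events in Phase 1 and 2a, though those studies were shorter. The 8-13% also needs null (a), in which response among the biopsied rises with dose and missingness exactly offsets it. Both points stand. The figures show how far the two sets can diverge; they do not predict that they will.

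Fourth, the trial is Phase 2 and makes no multiplicity adjustment. The primary test nevertheless has a stated 0.05 level, and Protocol 6.2.1 says this study feeds Phase 3 design and dose selection.

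**Conclusion.** Wrong as written. SAP 7.2 states a membership condition that conflicts with SAP 5.0, 6.1.1 and 6.1.2 and Protocol 9.5.2.1 and 9.5.2.3. It gives no other rule for the roughly 160, and it leaves the order of the two runs unstated.

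Three stronger inferences are not supported:

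- **That the sponsor has replaced the primary analysis with the completer analysis.** The reference to mITT and the parallel wording of SAP 7.1 and Protocol 9.5.7 make a timing cut-off more likely.
- **That the test's false-positive rate is 8-13%.** That holds only for missingness rising with dose under null (a). Other assumptions give about 5%, or 1.6-3.1%.
- **That the biopsied-only set always flatters the drug.** Against 25 points, the 40 mg minus placebo difference reads 31.3-34.2 with rising missingness and 27.8 with equal 10%, but 23.4-24.5 with reversed missingness.

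All of these sizes rest on assumed missing-biopsy rates. The contradiction in the text does not.

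**What to change.** SAP wording only, settled before the Week 24 unblinding.

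1. In 7.2, delete the closing words that limit the efficacy bullet to biopsied participants. State that SAP 5.0 and 6.1.1 govern, with the biopsied-only set as the completer analysis.
2. Name as primary the analysis of all dosed participants among the 197, run once Week 24 and ET biopsies are in, including the delayed ones that 7.2 accepts. Label the run on about 160 at 29 May 2020 early and supportive. State in 7.3 that the Week 24 histology endpoints are rerun.
3. For the early run, define membership by a fixed first-dose date that does not depend on having a biopsy. First dose on or before 1 December 2019 would let both windows close by the cut-off. Report pending biopsies by arm, separately from missing ones, and show results with pending biopsies counted as failures and not so counted. If the sponsor prefers the early run as primary, it must state in advance how pending biopsies are handled; otherwise the non-responder rule would turn COVID-19 delays into failures in the main result.
4. Align SAP 2.5 with 7.2 and record the departure from Protocol 9.5.7. Correcting the statement in 7.2 that enrolment continues is editorial.

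**Cost.** The early set may not be exactly 160, and the formal result comes later. If the last participant was dosed by 30 January 2020, nominal Week 24 falls by 16 July 2020 (+168 days). Waiting for every biopsy acceptable up to Week 48 could extend to 31 December 2020 (+336 days).

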7.3 Week 52 Analysis

Sponsor and designee personnel may be unblinded once all participants have completed the Week 52/PTFU visit and all data have been collected through that time point to facilitate analyses. The list of TFLs to be provided for this analysis will be kept in a separate document outside the SAP.

7.4 Long-term Follow-up Analysis

Data collected after the Week 52/PTFU visit (or early termination) will be reported in a separate analysis once all participants have completed long term follow-up. The list of TFLs to be provided for this analysis will be kept in a separate document outside the SAP.

Sponsor: Bristol-Myers Squibb

Protocol no: MB130-068

7.5 Exploratory Analyses

Any exploratory analyses completed to support study analyses in the Clinical Study Report (CSR), which were not identified in the statistical analysis plan, will be documented as such in the CSR.

8.0 Conventions and General Definitions

8.1 General Definitions

Term	Definition
Study Day	Study day is calculated as: assessment date – date of first dose + 1
Baseline	Unless otherwise stated, Baseline is defined as the last measurement prior to dosing on Day 1 (Week 0). If the measurement on Day 1 is missing or not available, then a prior measurement during the screening period may be used as baseline.
Change from Baseline	Change = Value at post-baseline visit – value at baseline
Change in the maximum post-baseline value	Change = Highest observed value post-baseline – value at baseline
Percent Change from Baseline	Percent change from baseline is defined as ([value at post-baseline visit – value at baseline]/value at baseline) x 100. If the baseline value is 0 and the post-baseline value is also 0, then the percent change from baseline is set to 0.
Study Treatment	For the purposes of the calculations included in this SAP, study treatment will include only doses of BMS-986036 (dose levels of 10 mg QW, 20 mg QW or 40 mg QW) or placebo QW.
Duration of Study Treatment	Duration of study treatment in weeks will be defined as: (date of last dose of study treatment – date of first dose of study treatment+7)/7.
Treatment Completion (%)	Treatment completion (%) will be calculated as the total number of treatment doses received divided by the total number of expected doses (48), multiplied by 100.
End of Study (EOS) Date	The EOS date is the date recorded on the eCRF that a participant either discontinued or completed the study. If the participant is lost to follow-up, the EOS date will be the date of the last visit assessment obtained.
First Dose Date – Study	The date a participant received their first dose as recorded in the eCRF as date study treatment was administered.
Last Dose Date – Study	The date of last recorded dose on the eCRF for a subject.
Unscheduled assessments	Unscheduled measurements will be included in the listings. With the exception of unscheduled measurements used for baseline and unscheduled measurements will be excluded from the descriptive statistics and statistical analysis.

Sponsor: Bristol-Myers Squibb

Protocol no: MB130-068

Prior, Concomitant, and Follow-up Medications	Prior medications are defined as medications taken prior to the first dose of study treatment and discontinued prior to the first dose of study treatment. Concomitant medications are defined as any medication started before/on/after the first dose of study medication until the Week 52/PTFU Visit. Follow-up medications are defined as any medication taken after Week 52/PTFU Visit until the 6 Month Post PTFU Visit that could potentially impact bone mineral density assessments. Any Concomitant medications continued Post Week 52/PTFU will also be considered as Follow-up medication.						
---	---	--	--	--	--	--	--

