Any pregnancy that occurs in a female partner of a male study participant should be reported to sponsor or designee during at least 5 half-lives after product administration (5 days) plus 30 days (duration of ovulatory cycle) for a total of 35 days after the end of the Double-Blind Treatment Period. In order for the sponsor or designee to collect any pregnancy surveillance information from the female partner, the female partner must sign an ICF for disclosure of this information. Information on this pregnancy will be collected on the Pregnancy Surveillance Form.

Laboratory Test Result Abnormalities

The following laboratory test result abnormalities should be captured on the nonserious AE eCRF page or SAE eCRF page, as appropriate. Paper forms are to be used only in the event that the electronic system is not functioning.

- Any laboratory test result that is clinically significant or meets the definition of an SAE
- Any laboratory test result abnormality that required the participant to have study medication discontinued or interrupted
- Any laboratory test result abnormality that required the participant to receive specific corrective therapy

It is expected that wherever possible, the clinical rather than laboratory term would be used by the reporting investigator (e.g., anemia versus low hemoglobin value).

Potential Drug-Induced Liver Injury

Wherever possible, timely confirmation of initial liver-related laboratory abnormalities should occur prior to the reporting of a potential DILI event. All occurrences of potential DILIs, meeting the defined criteria, must be reported as SAEs (see Appendix 8 for reporting details). **Repeat laboratory testing may be performed locally**, and the results should be promptly communicated to the investigator site.

For the purpose of evaluating a potential DILI, the Baseline value is defined as the mean of the test results from analysis of samples collected during Screening and on Day 1.

Note that the evaluation processes below do not replace SAE reporting per defined criteria in [Appendix 8](#).

Evaluation of Participants with New Elevations of Aminotransferases and/or Total Bilirubin

Repeat laboratory testing (including ALT, AST, fractionated bilirubin and alkaline phosphatase) and physical examination should be performed within 48-72 hours when:

- Participants with normal Baseline aminotransferase (ALT and/or AST) values develop elevations greater than $3\times$ the ULN based upon the central lab, or

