4.3.5 Clinical Laboratory Parameters

- Absolute and change from baseline values at each visit through Week 52/PTFU
- Potential hepatotoxicity by time point
 - Aspartate aminotransferase (AST) or alanine aminotransferase (ALT) > 3 x upper limit of normal (ULN) or > 5 x ULN
 - Total Bilirubin > 2 x ULN
 - (AST or ALT) >3 x ULN and Total Bilirubin > 2 x ULN

Sponsor: Bristol-Myers Squibb

Protocol no: MB130-068

- Post-baseline abnormalities defined by the below categories:
 - Serum albumin < 2.8 g/dL
 - Platelet count < 75 x 10³/ µL
 - Fasting plasma glucose <60 mg/dL or >350 mg/dL
 - Fasting triglycerides > 500 mg/dL
 - Estimated glomerular filtration rate (eGFR) < 30 mL/min/1.73 m²

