6.2 Safety Analyses

6.2.1 Adverse Events

All adverse events will be presented based on the safety population by treatment group, and pooled BMS-986036.

A summary of treatment-emergent AEs, including the number of events reported and the number and percentage of participants reporting

- at least one AE
- any severe AE
- any treatment-related AE
- any AEs of special interest
- any severe treatment-related AE
- any AE with outcome of death

Sponsor: Bristol-Myers Squibb

Protocol no: MB130-068

- any serious AE
- any treatment-related SAE
- any AE leading to the discontinuation of study treatment
- any treatment-related AE leading to the discontinuation of study treatment
- any AE leading to discontinuation of the study
- any treatment-related AE leading to discontinuation of the study

A breakdown of the number and percentage of participants reporting each AE, categorized by system organ class (SOC) and preferred term (PT) will be presented. Maximum severity will be summarized for all TEAE by SOC and PT. Counts for AEs will be by participant not event and participants are only counted once within each SOC or PT.

Only treatment-emergent AEs will be summarized in tables. All AEs will be included in listings. In addition DILI will be presented graphically.

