6.2.4 Clinical Laboratory Parameters

Based on the safety population, continuous laboratory results will be summarized by visit, treatment group, and pooled BMS-986036. Categorical results such as those for urinalysis will be summarized by number and percentage of participants in each category. These summaries will be based on central laboratory results, except in rare circumstances in which only a local lab value is available then a local lab value may be used. This value will be presented in the same unit and summarized with the central results from other participants. Summaries will present both actual and change-from-baseline results for continuous values.

Sponsor: Bristol-Myers Squibb

Protocol no: MB130-068

The participants with abnormal post-baseline values of laboratory parameters (with available threshold values) will be descriptively summarized by counts and percentages by time point.

Laboratory values below the lower limit or above the upper limit of quantification will be imputed to the lower or upper limit, respectively, for summary tables. The actual values will be displayed in the listings.

Box plots will be presented by time point. All laboratory data specified in the summary tables will be present in listings.

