8.3 Visit Windows

Visit windows as defined in the protocol are closely monitored by clinical monitors. A protocol deviation will be documented if assessments were recorded outside the visit windows, but the assessment is recorded in the clinical database at the planned visit. For longitudinal summaries of data, assessment recorded at the planned visits in the clinical database are included and displayed in tables with visit based structure.

If there are multiple records within the same visit window, then the value in the visit window closest to the day of the planned visit is selected.

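### Liver threshold crossings seen only on an off-schedule retest can be missing from the SAP's hepatotoxicity counts by arm

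*SAP*

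**What the plan says.** **Unscheduled results.** SAP 8.1 sends them to the listings and continues: "With the exception of unscheduled measurements used for baseline and unscheduled measurements will be excluded from the descriptive statistics and statistical analysis". The sentence does not parse, and words may have dropped out. As it stands, the only exception that can be read is use as baseline.

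**Liver counts.** SAP 4.3.5 heads its liver categories "Potential hepatotoxicity by time point". They are ALT or AST above 3 × and above 5 × ULN, total bilirubin above 2 × ULN, and ALT or AST above 3 × ULN together with bilirubin above 2 × ULN (the combined row). SAP 6.2.4 says that abnormal post-baseline laboratory values "will be descriptively summarized by counts and percentages by time point".

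**Which record is tabulated.** Under SAP 8.3, "assessment recorded at the planned visits in the clinical database are included and displayed in tables with visit based structure". If several records share a visit window, the one nearest the planned day is taken, not the worst.

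**Local values.** SAP 6.2.4 bases its summaries on central results, "except in rare circumstances in which only a local lab value is available then a local lab value may be used".

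**Other liver displays.** SAP 6.2.1 adds: "In addition DILI will be presented graphically". It does not say which results are plotted. SAP 8.1 defines a highest post-baseline value, but no section of the SAP text applies it.

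**Retests.** Under protocol 8.5.3.1, repeat liver tests "and physical examination should be performed within 48-72 hours when" one of two triggers is met, one for normal and one for elevated baseline aminotransferases. If the elevation persists without symptoms, laboratory checks follow two or three times a week and may drop to weekly or less once stable. A separate rule for stopping or interrupting study medication requires a full repeat liver profile on the same 48-72 hour scale. On location, the protocol says: "Repeat laboratory testing may be performed locally".

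**The concern.** The protocol's retests are the draws that follow a rising liver signal, and they fall between planned visits. The SAP's liver counts are built from planned-visit records, and its general rule keeps other post-baseline results out of the statistics. The draws most likely to show the peak are thus the ones most exposed to exclusion.

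The rows affected are the most severe liver laboratory counts in the SAP: above 5 × ULN and the combined row, with bilirubin above 2 × ULN beside them. They are rare-event rows, where the difference between none and one in an arm is most of what the row conveys.

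**Working it through.** No planned figure has to be reproduced. The check applies the SAP's rules to the protocol's retest scheme.

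**1. Timing.** Chemistry is taken at Weeks 4, 8, 12, 16, 20, 24, 32, 40, 48 and 52: ten planned post-baseline time points, 28 or 56 days apart. A retest comes 2 to 3 days after the trigger. A participant without symptoms whose elevation persists then has 2-3 draws in the first week of close observation. That makes 1 + 2 = 3 to 1 + 3 = 4 results, none of which enters the counts if recorded as unscheduled.

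**2. One case followed through the rules (assumed values, × ULN).** Week 24: ALT 3.4, bilirubin 1.1. Retest 3 days later: ALT 6.0, bilirubin 2.3. Week 32: ALT 1.2, bilirubin 0.8.

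| Row | SAP rules | All post-baseline results |
|---|---|---|
| ALT/AST > 3 × ULN | yes | yes |
| ALT/AST > 5 × ULN | no | yes |
| Bilirubin > 2 × ULN | no | yes |
| Combined | no | yes |

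**3. Which retest routes can produce this.** The table assumes that the triggering draw was at a planned visit and is therefore counted.

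| Route (protocol 8.5.3.1) | Already present at the trigger | Can first appear on retest |
|---|---|---|
| Normal baseline | ALT/AST > 3 × ULN; no bilirubin condition | > 5 × ULN, bilirubin, combined |
| Interruption rule, scenario 1 | ALT/AST > 2 × baseline and > 3 × ULN, with bilirubin > 2 × baseline, an INR rise > 0.2, or symptoms | > 5 × ULN, bilirubin, combined |
| Interruption rule, scenario 2 | Bilirubin > 2 × ULN with symptoms; no ALT/AST level | Bilirubin row already met; only an ALT/AST crossing could be new |
| Elevated baseline | ALT/AST > 2 × baseline and > 200 U/L, with bilirubin > 2 × ULN | Bilirubin row already met; the rest depends on ULN |

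For the last route the documents give no ULN. A value above 200 U/L exceeds 3 × ULN if ULN is at most 200/3 = 66.7 U/L, and the combined row is then met on the triggering draw. It exceeds 5 × ULN only if ULN is at most 200/5 = 40 U/L. With an assumed ULN of 45 to 60 U/L, the > 5 × ULN row needs a value above 5 × 45 = 225 to 5 × 60 = 300 U/L, which a retest could be the first to show.

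**4. Can the nearest-day rule in SAP 8.3 rescue the retest?** Suppose, against 8.1, that a retest may compete for the visit window. Let the visit fall d days from plan (d = -5 to +5) and the retest 2 or 3 days later. The retest is chosen when |d + 2| < |d|, or |d + 3| < |d|. Both hold for d = -5, -4, -3 and -2 only, which is 4 of 11 offsets; in the other 7 it is not chosen. Most later close-observation draws fall outside the ±5-day window.

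**5. Size of one missed case (illustration).** Arm size is 197/4 = 49.25, about 49; pooled active is 197 × 3/4 = 147.75, about 148. In an any-time row:

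- per arm: 0/49 (exact 95% CI 0 to 7.3%) instead of 1/49 = 2.0% (0.05 to 10.9%)
- pooled: 0/148 (0 to 2.5%) instead of 1/148 = 0.7% (0.02 to 3.7%)
- Week 24 analysis, about 160/4 = 40 per arm: one case is 1/40 = 2.5%

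**The case against.** **The 8.1 sentence may have lost a second exception, and the table shells are not visible.** Both are true. An any-time liver row may exist in the separate shells. If so, it would contradict 8.1 as written, and the SAP would still need to say which governs.

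**The signal is captured elsewhere.** This largely stands. Protocol 8.5.3.1 requires any clinically significant laboratory result to be recorded as an adverse event, and potential DILI is reported as an SAE. Adverse events are tabulated by arm, unscheduled values are listed, a DILI figure is planned and the data monitoring committee reviews safety. A participant who discontinues also has early-termination chemistry, which may catch a persisting peak. A reader might infer that severe liver events would vanish from the report, but the documents do not support that. What is missing is narrower. The adverse event tables are by system organ class and preferred term and do not show which threshold was crossed. The potential-DILI definition in protocol Appendix 8 is stricter than the combined row, since it also excludes initial cholestasis and other apparent causes. Listings give no count by arm.

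**Local retests.** A reader might infer that the local-value clause in SAP 6.2.4 excludes local retests on a second ground. The text does not settle this. Read draw by draw, a retest done only locally has no central counterpart, so the clause could admit it. The clause also refers to the summaries described before it, whereas the abnormal-value counts come in a later paragraph. This is an ambiguity to resolve, not support for the point.

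**By-visit tables are right to leave out extra draws.** Agreed. Retested participants have more chances to cross a threshold, so the by-visit tables should stay.

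**Conclusion.** The point holds as a gap in the counts by threshold and arm. On the SAP text as it stands, a > 5 × ULN peak, or a bilirubin rise that fills the bilirubin or combined row, can be left out when only an off-schedule retest shows it. It applies mainly to the normal-baseline trigger and to scenario 1 of the interruption rule. It would be too strong to say that every retest route exposes all three rows: under scenario 2 and the elevated-baseline trigger, bilirubin above 2 × ULN is already present at the triggering draw.

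The documents give no rate, so the number of participants affected is unknown. The 0/49 against 1/49 comparison describes an any-time row that the SAP text does not contain. Its own rows are by visit, and SAP 6.5 lets denominators follow the number still in the study. The two intervals overlap almost entirely, and no test is planned on these rows.

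The conclusion assumes that retests are recorded as unscheduled and that the shells add no any-time count. Confidence is medium for those reasons. The change is still worth making, because a stated rule can undercount the most severe liver categories and the correction is cheap.

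**What to change.** 1. Rewrite the 8.1 sentence so that it parses, and limit the exclusion of unscheduled results to by-visit summaries.
2. Add to 4.3.5 and 6.2.4 one table, by arm and pooled, of participants whose worst post-baseline value meets each hepatotoxicity category. Use every result, scheduled or unscheduled, central or local, with local values judged against their own ULN.
3. For the combined row in that table, state how close in time the aminotransferase and bilirubin values must be.
4. State in 6.2.4 how a local-only retest is treated, and in 6.2.1 that the DILI figure uses the same data as the new table.
5. Keep the by-visit tables beside it, so that the unequal number of draws is visible.

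The cost is SAP wording and one table. SAP 8.1 already sends unscheduled results to the listings, so no new data are needed, but local ULNs must be available. No clinical rule changes.
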